1. SUMMARY OF TRIAL

Of the 48,000 breast cancers diagnosed annually in UK, almost 60% of patients undergo breast conserving surgery (BCS). Surgical removal of the cancer aims to reduce the risk of local recurrence and patient mortality. In order to minimise the amount of tissue removed, excision up to the cancer-free area (margins) is undertaken. Further surgery following BCS is required in 25% of patients with invasive cancers with surrounding DCIS and 30% of DCIS patients because of disease found at the edges of the tissue removed.

Reducing the need for further operations benefits patients (by reducing the number of operations required, minimising anxiety) and the NHS (by realising economic benefits).

MarginProbe, a disposable probe which measures the margins of tissue removed during BCS surgery, allows the surgeon to remove further tissue during the same surgical procedure to clear any involved margins, minimising subsequent re-operations.

Four hundred and sixty patients in 6 specialist Breast Units will be randomly allocated peroperatively after BCS (and specimen radiology), by telephone randomisation, to either:

- MarginProbe assessment of the surgical specimen with re-excision of margins if required;

- Standard BCS (clinical and radiological clear margins) whereby the wound will be closed and the surgery completed (standard UK practice).

The primary aim of the study is to determine whether the MarginProbe device reduces the need for second surgical procedures (and improves margin clearance by \geq 1mm) by enabling the removal of involved margins during the same procedure.

Main outcome: number of people requiring second re-excision surgery within 9 months of their first BCS. We will also look at the impact on quality of life, cosmetic appearance and the results of laboratory assessments of removed tissues.

The health related quality of life and cosmetic appearance of the surgery (photographs of 2 views - front/side) will be compared by researchers who do not know which treatment people received.

AIM

Surgical excision of breast cancer and surrounding ductal carcinoma in situ (DCIS) aims to reduce the risk of a local recurrence and increased mortality of the patient, by excising the cancer with cancer-free margins. Surgical practice in the USA allows for examination of frozen tissue section taken during breast conserving surgery to identify involved or close cancer margins.

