Margin status is assessed histopathologically according to the NHS Breast Screening Programme Quality Assurance Pathology Guidelines[17] and its width is measured with a micrometer. Specimen radiography is routinely used to identify the closest margin and surgeons re-excise during the initial operation if a margin is close on specimen radiography. NICE guidelines mean most Breast Units schedule a re-excision operation if the margin circumferentially is less than 1mm from any edge on final histopathology, at additional costs to patient and NHS[2].

For DCIS and cancers with surrounding DCIS identified on core biopsy and/or mammography, the re-excision rate ranges between 23-37%. Nationally after BCS, despite specimen radiology showing clear margins and this is the group to be studied in this trial. As re-excision rates may differ between Trusts, we will stratify randomisation for each Breast Unit and for the presence or absence of invasive cancer with DCIS. Additionally, each Unit has agreed to use 1mm as the clear margin cut-off when deciding the need for re-excision in the MDT meeting.

The MarginProbe device utilises a probe which when placed on an excised specimen in theatre, detects involved margins, thereby allowing immediate re-excision during the same surgical procedure and optimising surgical outcome by reducing the need for repeat operations to achieve clear margins[7]. The device measures a tissue area of 7mm to a depth greater than 1mm which, requiring repeated margin measurements, allows multiple points of the specimen to be sampled in approximately 10 minutes.

In a randomised, prospective, multi-centre trial carried out in Israel encompassing 300 patients, device use produced a 56% reduction in re-excision rate[9] when excluding patients who underwent subsequent mastectomy and positive margin width assessment was not different at

1mm or 2mm thresholds. There was no significance in device sensitivity for different cancer types including DCIS, invasive, ductal and lobular cancer[7,9] and no significant difference in long-term cosmetic outcome between groups when evaluating patients in both groups.

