It should be the aim of conservation surgery to achieve clear excision margins. Any patients who do not have a clear excision require re-excision. Patients should be counselled about this possibility at the time of diagnosis. Because of the difficulty of assessing margins, all patients undergoing breast-conserving surgery should have directed cavity biopsy shavings taken to assess excision (See Surgical Principles under 'Trials Procedures').

Randomisation procedure: Simple individual randomisation will be undertaken by telephone, after prior arrangement via The MAHSC-CTU. Women will be randomised in theatre, by call to the CTU after completion of excision and specimen radiology, to either standard procedure (no further surgery, close wound) or the use of the MarginProbe device on the excised specimen to determine whether margins are involved and further re-excision is required.

Patients must be randomised between 9am-4.30pm Monday-Friday. If there are any changes to the MAHSC-CTU randomisation line opening hours, sites will be informed. It is important that sites take this into consideration when approaching patients/ planning surgery lists. Randomization will take place immediately after the main ex-vivo lumpectomy specimen has been excised, oriented, centre marked, inspected, palpated, and additional cavity shavings performed and documented.

Blinding and bias: Leaving randomisation until after excision will minimise bias that may occur in surgical procedure and thus also removes need for using a cluster design. Clearly, we cannot blind the surgical team to allocation once it occurs and we will not blind women to whether or not they received MarginProbe as this is likely to be viewed unfavourably by an Ethics Committee and it is only through knowing allocation that any expectation effect may occur amongst those who do receive MarginProbe. We recognise that a disappointment bias may affect the control group and we will guard against this by ensuring information about benefits to taking part in RCTs are available to both groups. After written informed consent, the surgical team will liaise with the MAHSC-CTU so telephone randomisation in theatre can be planned and without delays.

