The Breast Screening Centres selected treat over 2,600 cancers each year of which over 1,800 will require BCS. In this group of patients, 50% agree to participate in treatment trials, however, we would expect a higher rate as this trial does not involve patients having to take additional trial medication and similar non-medical intervention trials have recruited up to 60% in Manchester. Thus we expect to recruit the required number of 460 patients within one year from the participating centres. We would not expect loss of population due to death as these patients will be fit for anaesthetic and survival is in excess of 98% at 10 years.

Randomisation: Allocation of patients to either standard procedure or the use of the Margin Probe device in a 1:1 ratio will be made using the method of simple permuted block randomisation (with random block sizes) .Patients will be individually randomised by telephone via the MAHSC-CTU.

Baseline data: Patient characteristics will be summarised using numbers and percentages for qualitative data, medians and ranges for ordinal qualitative data and non-Normal continuous data, and means and standard deviations for Normally distributed continuous data. Normality will be assessed by inspection of distribution graphs and skewness/kurtosis statistics.

Primary Endpoints: The re-excision rate (at least one further surgical re-excision operation by 9 months) between the two groups will be compared initially using the simple chi-square test followed by logistic regression analysis (to adjust, if necessary, for any potential confounding factors e.g. Centre; DCIS vs invasive). Total numbers of re-excisions will be compared using generalised linear models with Poisson or Negative Binomial regression. The percentage of patients with excision margins \leq 1 mm after one BCS procedure will be compared using logistic regression analysis.

Secondary Endpoint: Tissue weight excised will be compared initially between the two groups using the simple t test followed by linear regression analysis (to adjust, if necessary, for any potential confounding factors e.g. Centre; DCIS vs invasive). Ordinal regression will be used to compare the cosmetic evaluation scales.

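### The stratified randomisation promised in the Background is missing from both operative randomisation paragraphs, and the protocol does not say whether the unadjusted or the adjusted primary result decides the trial

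*Protocol*

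**What the plan says.** **Allocation** is described in three places in the protocol.

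- Section 2 (Background) gives a reason, "As re-excision rates may differ between Trusts", and then the promise: "we will stratify randomisation for each Breast Unit and for the presence or absence of invasive cancer with DCIS".
- Section 3 (Trial Design, Randomisation procedure): "Simple individual randomisation will be undertaken by telephone, after prior arrangement via The MAHSC-CTU". No blocks or strata are named.
- Section 4 (Data Analysis and Statistical Considerations, Randomisation): 1:1 allocation "will be made using the method of simple permuted block randomisation (with random block sizes". Blocks are named, but no strata.

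**Primary analysis** is in section 4 (Primary Endpoints). The proportion with at least one re-excision by 9 months "will be compared initially using the simple chi-square test followed by logistic regression analysis". The regression is there to adjust, if that proves necessary, for potential confounders. Centre and DCIS versus invasive cancer are given only as examples.

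**Size** is in section 1: "Four hundred and sixty patients in 6 specialist Breast Units".

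**The concern.** The only promise to stratify sits in the Background. A trials unit building its system from section 3 or section 4 would have no instruction to stratify, and the balance by unit and histology that the Background asks for would be left to chance.

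The analysis wording adds a second loose end. The protocol does not say what makes adjustment necessary, does not close the covariate list, and does not name the deciding result. In an unblinded trial, that leaves room to prefer whichever of two results is more favourable. A statistical analysis plan might narrow this, but the conditional rule is stated in the protocol itself, and so is the conflict over allocation.

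The stratum is also loosely worded. The inclusion criteria admit HER2-positive invasive cancer with or without DCIS, and lobular cancer without DCIS. Under the Background's phrase these patients could be grouped with the invasive cancers or with everything that is not invasive-with-DCIS.

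**Working it through.** **1. The plan's own figure.** Inputs from section 4: 25% versus 12.5%, two-sided 5%, 90% power, continuity correction.

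- Mean proportion 0.1875. Without correction, n = [1.960 × √(2 × 0.1875 × 0.8125) + 1.282 × √(0.25 × 0.75 + 0.125 × 0.875)]² / 0.125² = (1.082 + 0.698)² / 0.015625 ≈ 202.8, so 203.
- With correction, n = (202.8/4) × [1 + √(1 + 4/(202.8 × 0.125))]² ≈ 218.5, so **219 per group**, as stated. The sample size is not in question.

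**2. Balance lost without strata.** Inputs: 460 patients, 6 units (assumed equal in size), 20% DCIS.

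- Patients per unit: 460/6 ≈ 77. Under simple randomisation the SD of the number in one arm is √77/2 = 4.4, so the 95% range is about 30 to 47 around 38.5.
- DCIS patients per unit: about 15, with SD √15/2 = 1.9.
- Difference between arms in DCIS share: SD = √(0.2 × 0.8 × 2/230) = 3.7 points, 95% range about ±7 points. With blocks inside the 12 unit-by-histology strata, the simulated SD is about 0.9 points.
- Consequence: the protocol's rates for DCIS and invasive cancer are 30% and 25%. A 7-point imbalance therefore shifts the crude difference by about 0.07 × 5 = 0.35 points, against a target difference of 12.5 points.

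**3. Precision lost by ignoring strata after stratified blocks.** The protocol gives no rates per unit, so the ranges here are assumptions, with six evenly spaced units.

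- Control-arm variance only: standard error ratio = 1/√(1 − v/0.1875), where v is the between-unit variance. For 16–37%, v = 0.00515 and the ratio is 1.014. For 10–42%, v = 0.01195 and the ratio is 1.033.
- Both arms, with rates halved in every unit on the device: ratio = 1/√(1 − 1.25v/[p(1−p) + (p/2)(1−p/2)]), where p is the mean control rate. For 16–37% (p = 0.265) this is 1/√(1 − 0.00643/0.3097) = 1.011. For 10–42% (p = 0.26) it is 1/√(1 − 0.01493/0.3055) = 1.025.

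**4. Simulated type I error and power, stratified blocks.** 460 patients, 6 units, 20% DCIS; uncorrected chi-square versus a Mantel-Haenszel test over 12 strata; 6,000 null and 2,000 alternative trials per scenario; Monte Carlo SE of type I error about 0.003.

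| Assumed unit rates | Type I error, unadjusted / adjusted | Power at a halved rate, unadjusted / adjusted |
|---|---|---|
| 18–32% | 0.055 / 0.056 | 94.2% / 94.2% |
| 10–40% | 0.045 / 0.053 | 94.3% / 94.8% |

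**5. Cost of leaving the choice open.** Same set-up, with unit rates of 18–32%, 16–37% and 10–40%; 8,000 null and 3,000 alternative trials per scenario.

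| Allocation | Type I error if either result may be claimed | Tests disagree on significance (40% relative reduction) |
|---|---|---|
| Simple or unstratified blocks | 5.7–6.5% | 4.0–6.5% |
| Stratified blocks | 4.9–5.0% | about 1.3% |

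The Monte Carlo SE of these type I error figures is about 0.25 points. They use only the two covariates that the protocol names. A longer list would widen the choice.

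**The case against.** The strongest reply is that the three descriptions can be reconciled. *Individual* may simply mean not by cluster, since section 3 discusses and dismisses a cluster design in the same context. *Simple* is used loosely throughout (simple chi-square, simple t test). Random-size blocks can sit inside unit and histology strata, and the word unstratified appears nowhere. This stands to the following extent: a reader might infer three mutually exclusive schemes, or that allocation was in fact unstratified, and the document supports neither. It supports only that the operative paragraphs omit the promised factors and that no passage joins the pieces together.

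On the analysis, section 4 does fix an order, the chi-square belongs to the test family used for the sample size, and the two Background factors are already named as candidates for adjustment. A reader might infer that the unadjusted test is invalid or the trial underpowered. The calculations show otherwise: the test holds its level under all three descriptions, and chance imbalance does not bias the comparison. An order of tests is still not a statement of which one decides, and the condition for adjusting is undefined.

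On the stratum, the sample-size and analysis text already uses a plain split of DCIS versus invasive cancer. Only the Background phrase is ambiguous, so this is a minor point.

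**Conclusion.** The point holds in limited form. The protocol promises stratification in one place and omits it in the two places where it would be implemented, and it does not name the deciding primary result. The sample size is unaffected. The unadjusted test is at most slightly conservative after stratification, and the power difference at the planned effect is about 1 point or less. The measurable harm is modest: roughly 1 point of extra type I error if the choice of result is used and allocation is not stratified.

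The simulated figures rest on assumed unit rates and equal expected recruitment across units. The gains from fixing it are balance, reproducible allocation and one pre-declared primary result. That makes it something that should be fixed, not something that must be fixed for the trial to be valid.

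**What to change.** 1. State one scheme in the same words in section 2 (Background), section 3 (Randomisation procedure) and section 4 (Randomisation): permuted blocks of random size, stratified by Breast Unit and by DCIS alone versus any invasive cancer, with lobular and HER2-positive cancers without DCIS counted as invasive. The Background phrase must change too, or a conflict over the stratum remains.
2. In section 4 (Primary Endpoints), delete the *if necessary* condition. Name one primary analysis: a logistic regression (or Mantel-Haenszel test) of re-excision on arm, always adjusted for Breast Unit and DCIS versus invasive cancer. Keep the unadjusted chi-square as supportive.
3. If recruitment has begun, state the scheme actually in use and change only the analysis wording.

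The cost is an edit to the protocol, matching text in the analysis plan, and confirmation of the trials unit's randomisation specification. No extra patients or data are needed.

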TRIAL OBJECTIVES

Primary Objectives:

1. To determine if intraoperative margin assessment after excision of a cancer reduces reexcision procedures, compared to standard surgical practice by 9 months after primary surgery.2. To compare the total number of re-excision procedures required between groups and tissue weight resected after BCS, because of positive margins.

Secondary objectives:

- 1. To determine the effect of margin assessment on a) quality of life (QOL), b) cosmetic outcomes and cost-effectiveness (EQ5D).
- a) QOL in each group will be measured by using validated self-completion disease specific and generic instruments, FACT-B[11], HADS[12], health-related utility (EQ5D) and the body image scale of SABIS[13] administered at baseline (pre-surgery) and postal follow-up at 1,3,9 months post-surgery to permit calculation of Trial Outcome Index (FACT-B TOI). This assessment will permit area under the curve approach to analysis of differences between arms in QoL.[C1] Quality of life is a crucial variable if we are to understand the impact of MarginProbe, especially if the effect on re-excision rates is not of marginal significance. The effect of avoiding re-excision or mastectomy on the quality of life of women may act as a multiplier which makes the procedure worth (or alternatively not worth) undertaking even if the actual numbers of excisions and mastectomies avoided is marginal.
- b) Cosmetic evaluation, blind to randomisation assignment will be conducted at baseline and 9 months by observer using a symmetry based scale[14] and photographic measurements compared by observers blinded to randomisation. Two independent observers will use the symmetry-based ratings and undertake the photographic measurements to assess cosmetic outcomes. Inter-rater agreements will be calculated to check reliability of observations. Patient related outcomes will be measured using the Harvard Cosmesis Scale[21].

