Histopathological assessment of margin status will utilise micrometer measurement of margin clearance according to standard NHSBSP pathology guidelines protocols[17]. NHSBSP minimal pathology datasets requires margin width to be measured at specimen margins and all centres have agreed they will only offer further surgery if margins are less than 1mm width at a circumferential (radial) margin. CRFs will record margin width, pathological size, extent of surrounding DCIS, grade and steroid receptor status, HER2 status (invasive cancers), together with the Multidisciplinary Meeting decisions about need and reason recorded for any further surgery being offered to the patient. All specimens will be weighed and total specimen weight compared between groups. Fidelity checks for probe use according to randomisation and correct, probe-guided re-excision will be made. Independent review of pathology and fidelity checks will be supervised by the Lead Pathologist, [name].

Pathology

Pathology assessment is identical for both study arms. Histological examination of all tissue removed during the initial lumpectomy procedure and during any repeated surgery (repeat lumpectomy or mastectomy) will be blinded to subjects' treatment arm. Surgeons should coordinate with pathologists in order to ensure that orientation conventions are agreed upon and that pathologists' interpretation of margin boundaries (Medial, Lateral, Inferior, Superior, Anterior and Deep) are similar to those of the surgeon.

Each margin shall be inked in different colour, using the boundaries marked by the surgeon.

Routine processing will be performed on all tissue removed during the initial lumpectomy procedure. The pathology report will include the following:

- a) Microscopic margin width ("D") as well as the exact orientation, malignant content, and margin status of all tissue removed during the initial lumpectomy. D will be noted in increments of at least 0.5 mm up to 2 mm, and in increments of at least 1 mm in the range 2-10 mm.
- b) Dimensions of all specimens (main ex-vivo lumpectomy and Shavings)

Pathology data for ipsilateral breast surgical procedures (repeat lumpectomy / mastectomy procedures) will be also collected. In mastectomy procedures, margin status is not required; however all other data shall be included.

Specific harmonized study related requirements for pathology examination and for pathology data reporting are detailed in the pathology Standard Operating Procedure (Appendix 2).

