These may be either through the UK screening programme from the Nightingale Centre or lesions on mammograms requested for other reasons. Ultrasound guided surgery or needle localisation surgery is used. In the former the surgeon removes the area of breast tissue at a depth calculated by the scan, consistent with the scan findings. At needle localisation a volume of tissue is removed together with the wire.

- 1 In both cases liga-clips must orientate the specimen. One clip is used superiorly, two clips laterally and three inferiorly if this is written fully on the card then the radiologist will be able to ascertain the orientation of the specimen. It must also be recorded on the operation note.
- 2 The biopsy cavity site must be orientated with 4 ligaclips, superiorly, inferiorly, medially, laterally. This is important for the planning of adjuvant radiotherapy.
- 3 The excised specimen must be weighed and recorded in the operation note
- 4 Shavings must be taken from the adjacent breast tissue and sent separately. The shavings may have a sutures placed on the biopsy (inner) cavity surface to allow the pathologist to orientate the shaving itself. Ligaclips cannot be used as they would interfere with the device.
- 5 All impalpable lesions must be visualized radiologically by the operating surgeon on the intheatre X-Ray machine. The specimen should be radiographed in two perpendicular planes for a radiological assessment of the completeness of excision. A comment on the completeness of excision based on the intraoperative image must be made in the operation note by the surgeon. If the biopsy is undertaken for microcalcification a comment must be made in the operation note relating to the presence of microcalcification in the X-Ray image of the excision specimen. Any concerns should be discussed with a Consultant intraoperatively.
- 6 It is mandatory to obtain an intraoperative X-Ray image of a radiologically guided WLE.
- 7 It is expected that intraoperative images of WLE specimens in palpable cancers will also be obtained. It is not routinely required to obtain an intraoperative images of biopsy cavity shavings but this may be helpful in cases where the main specimen radiograph does not show the malignancy.
- 8 Intraoperative images should be electronically sent to Radiology for formal radiological assessment and to inform the MDT discussion of the case and complete radiological assessment of the lesion.

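### The tissue-weight comparison leads with an unadjusted t test, although the main specimen is removed and weighed before randomisation, so precision is given up that the trial could have at almost no cost

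*Protocol*

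**What the plan says.** **The analysis.** Section 4, Secondary Endpoint: "Tissue weight excised will be compared initially between the two groups using the simple t test followed by linear regression analysis". The purpose of the regression is given as "to adjust, if necessary, for any potential confounding factors e.g. Centre; DCIS vs invasive".

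**The timing.** Section 3, Randomisation procedure: "Randomization will take place immediately after the main ex-vivo lumpectomy specimen has been excised, oriented, centre marked, inspected, palpated, and additional cavity shavings performed". The same section places the randomisation call after specimen radiology, and the Pre-Randomization list under Trials Procedures gives the same order for the main specimen and the shavings guided by inspection and palpation. The control allocation is described as "standard procedure (no further surgery, close wound". Only the device arm goes on to probe-guided shaving.

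**The weights.** Surgical Principles, item 3: "The excised specimen must be weighed and recorded in the operation note". Section 3, on histopathological assessment: "All specimens will be weighed and total specimen weight compared between groups". The MarginProbe Device section also refers to the weight of additional shavings.

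**The variable.** Trial Objectives, primary objective 2, words it differently: "tissue weight resected after BCS, because of positive margins". Weight therefore appears under a primary objective in one place and as a secondary endpoint in Section 4.

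**The concern.** The device can change only what is removed after allocation. Whatever came out earlier cannot depend on the arm, but it varies from patient to patient, and in an unadjusted comparison of totals all of that variation goes into the standard error. The pre-randomisation weight is in effect a baseline measurement of the outcome. The protocol treats quality of life in just this way, since Section 4 fixes an analysis of covariance on baseline scores, but it does not do so for tissue weight.

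The regression that follows does not clearly close the gap. Adjustment is conditional and is justified by confounding. Here the reason to adjust is precision, which applies whether or not the arms happen to be balanced.

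The result will be read as evidence on whether the device costs the patient extra tissue. Under the protocol a single positive reading on a face calls for a shave there, so extra tissue in the device arm is expected. The Health Economic Analysis section links removal of more than 10% of breast tissue to reduced body image scores. A non-significant t test could be taken to show that no extra tissue was removed when the comparison was merely imprecise.

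**Working it through.** **1. The plan's own figure.** The protocol gives no SD, target difference or power for tissue weight, so there is none to reproduce for this endpoint. The sample size does reproduce: 25% v 12.5%, two-sided 5%, 90% power gives 203 per group without continuity correction and 219 with it, as stated. The calculations below use the planned 230 per group.

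**2. General effect of adjustment.** Let rho be the within-arm correlation of pre-randomisation weight with total weight. Adjustment multiplies the standard error by sqrt(1 − rho²), which is worth 1/(1 − rho²) times the patients. The difference detectable with 90% power, in units of the outcome SD, is (1.960 + 1.282) × sqrt(2/230) × sqrt(1 − rho²). Unadjusted, this is 3.242 × 0.0933 = 0.302 SD. The documents do not give rho, so these values are assumptions:

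| rho | sqrt(1 − rho²) | SE smaller by | Equivalent patients | Detectable difference (SD) |
|---|---|---|---|---|
| 0.3 | 0.954 | 5% | 1.10× | 0.288 |
| 0.5 | 0.866 | 13% | 1.33× | 0.262 |
| 0.7 | 0.714 | 29% | 1.96× | 0.216 |
| 0.8 | 0.600 | 40% | 2.78× | 0.181 |
| 0.9 | 0.436 | 56% | 5.26× | 0.132 |

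A difference with 50% power by t test would have 54%, 62%, 78% and 99% power after adjustment at rho 0.3, 0.5, 0.7 and 0.9.

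**3. Index operation only.** If the control wound is closed after randomisation, a control patient's total equals her pre-randomisation weight. Assume a pre-randomisation mean of 50 g with SD 20 or 40 g, and device shavings averaging 10 g (SD 8 g) in 70% of the device arm.

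- Mean difference: 0.7 × 10 = 7 g.
- Variance added in the device arm: 0.7 × (8² + 10²) − 7² = 65.8, or 32.9 averaged over the two arms.
- t-test SE at SD 20 g: sqrt(400 + 32.9) × 0.0933 = 1.94 g. At SD 40 g: sqrt(1600 + 32.9) × 0.0933 = 3.77 g (3.75 g in simulation).
- Adjusted SE in both cases: sqrt(32.9) × 0.0933 = 0.53 g.
- Simulated rho is 0.96 and 0.99. Simulated t-test power for the 7 g difference is 96% and 47%; adjusted power is 100% in both.
- Share of tissue removed before randomisation: 50/53.5 = 93%.

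**4. All surgery to 9 months.** Add mastectomy in 10% v 5% (the health economic assumption) and other re-excision in 15% v 7.5%, which together make up the planned 25% v 12.5%. Assume re-excisions averaging 25 g (SD 15 g) and mastectomies averaging 300, 500 or 700 g (SD half the mean).

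| Pre-randomisation SD | Mastectomy mean | rho | SE, t test | SE, adjusted | SE smaller by |
|---|---|---|---|---|---|
| 20 g | 300 g | 0.22 | 8.45 | 8.25 | 2.4% |
| 20 g | 500 g | 0.14 | 13.80 | 13.69 | 0.8% |
| 20 g | 700 g | 0.10 | 19.10 | 19.02 | 0.4% |
| 40 g | 300 g | 0.41 | 9.04 | 8.24 | 8.8% |
| 40 g | 500 g | 0.26 | 14.22 | 13.74 | 3.4% |
| 40 g | 700 g | 0.19 | 19.49 | 19.15 | 1.7% |

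The pre-randomisation share falls to 46–64%. A few large mastectomy specimens then carry most of the variance, and the covariate cannot explain them.

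**5. Which weight is meant.** Primary objective 2 can be read as tissue taken after the first excision. Section 3 says total specimen weight, near a pathology text that also covers repeat lumpectomy and mastectomy. Section 4 says only tissue excised. Steps 3 and 4 show that the choice decides how much adjustment gains.

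**The case against.** The strongest reply is that the protocol already provides a regression, lists its covariates only as examples and so does not bar pre-randomisation weight, and that covariates for a secondary endpoint commonly belong in a statistical analysis plan, which is not shown. The first part stands: the covariate is left unnamed, not excluded, and it would be wrong to say the regression can adjust only for centre and histology. The reply does not dispose of the point, because the protocol itself fixes the unadjusted t test as the lead and makes adjustment conditional on confounding.

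Three further objections limit the point, and each stands.

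- **Size.** No correlation or SD is given. The multiples of the patient number in the table are conditional on an assumed rho, and they fail if the weight includes later mastectomy.
- **Variance model.** For the index operation the control residual is essentially zero while the device residual is not, so a common residual variance does not hold.
- **Recording.** The protocol requires specimens to be weighed and pre-randomisation shavings to be documented. It does not show that weights are stored by pre- or post-randomisation status.

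A reader might go further and infer that the t test is biased, or that chance imbalance in the main specimen invalidates it. The documents do not support that. Allocation is randomised, and chance imbalance is already reflected in the t test's standard error. Nor do they support calling weight the principal measure of harm, since blinded cosmetic assessment and body image are measured too.

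**Conclusion.** The point holds as a loss of precision, on an endpoint for which the protocol claims no power. The error rate of the planned test is not in question.

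For weight removed at the index operation, the value of the covariate follows from the order of events. The gain is likely to be large: in the assumed example the standard error falls from 1.94–3.75 g to 0.53 g. For weight over all operations the gain is small, about 0.4% to 9% under the assumed mastectomy weights. Across an assumed correlation of 0.3 to 0.9, it is about 5% to 56%.

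The gram figures illustrate; none comes from the documents. The recommendation does not depend on them, because prespecified adjustment costs almost nothing under either reading. The undefined weight variable needs settling first.

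**What to change.** 1. Reconcile primary objective 2, the histopathology text in Section 3 and the Secondary Endpoint text in Section 4 on which weight is compared and whether it is a primary or secondary matter.
2. For index-operation weight, replace the t test as lead analysis with a linear regression of total weight on arm. Prespecify as covariates the pre-randomisation weight (main specimen plus pre-randomisation shavings), Breast Unit and DCIS v invasive. Use robust standard errors, because residual variance differs by arm.
3. Report weight over all surgery to 9 months separately, with the same covariate. A further index-operation model for post-randomisation weight is unnecessary: with pre-randomisation weight in the model, it gives the same arm coefficient as total weight.
4. Confirm that the case report form separates pre- and post-randomisation specimen weights. If it does not, use main specimen weight alone as the covariate.

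The cost is a few sentences in Section 4 and a check of the form. The weighing is already required, and neither the sample size nor the conduct of surgery changes.
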